7.4. Visit Windows

If there are multiple planned assessments for any study procedure at a given time point, the latest nonmissing value will be used for summarization. Unscheduled assessments will be listed and will be used to flag baseline visit if this is the last non-missing assessment before the first dose of study drug, but unscheduled assessments will not be included in the summarization, unless to be used to avoid missing data at Week 16.

7.5. Pooling of Centers

Not applicable since no adjustment for center or by center analyses are planned.

7.6. Subgroups

Subgroup analyses only apply to some of the exploratory endpoints and are described in section 9.2.3.

8. Demographic, Other Baseline Characteristics and Medication

8.1. Patient Disposition and Withdrawals

The following frequencies (number and percent) will be displayed for all patients screened, patients randomized, screen failures, and reasons for screen failure.".

The analysis populations will be summarized with counts and percentages by treatment group. This table will include the following: number of patients screened, patients randomized, patients in safety population, reasons for exclusion from the safety population, patients in ITT population, reasons for exclusion from the ITT population, patients in PP population, and reasons for exclusion from the PP population.

The following frequencies (number and percent) will be displayed for all patients in the randomized population: patients in the safety population, patients in ITT population, patients in PP population, patients who completed the study (including follow-up), patients who discontinued early, study duration in days, patients who completed study treatment, patients who discontinued study treatment early also presented by reason for early discontinuation. The denominators will be the number of randomized patients.

A Kaplan-Meier plot of time to discontinuation of study treatment will be presented by treatment for the ITT population. Cumulative proportion of patients with discontinuation of study treatment by treatment group as a function of time since randomization will be presented for the ITT Population. Cumulative proportion of patients with discontinuation of study treatment group and reason for discontinuation as a function of time since randomization will be presented for the ITT population.

Listings of treatment assignments, including the subject's identification, date and time of randomization, and assignment to treatment, will be presented.

Patient disposition, COVID-19 visit impact, inclusion/exclusion criteria violations and exclusions from analysis populations will be listed by patient.

8.2. Protocol Deviations

All protocol deviations (minor and major) observed during the conduct of the study will be listed. Major protocol deviations (patients with at least one major PD overall and split by PD category), and minor deviations (patients with at least one minor PD overall and split by PD category) will be summarized by treatment group for all randomized patients.

8.3. Demographic and Baseline Characteristics

Demographic and baseline characteristics, including age, sex, child-bearing potential, race, ethnicity, asthma diagnosis, disease duration, height, body weight, and body mass index (BMI) will be summarized for the ITT population using standard descriptive statistics. This table will be repeated for the PP population.

Baseline efficacy assessments: EASI, IGA-AD, BSA, DLQI score, POEM, PGIS, skin pain NRS, sleep disturbance NRS, peak pruritus NRS, and pulmonary status NRS will be summarized for the ITT population. No formal statistical comparisons between populations will be performed. This table will be repeated for the PP population. Demographics will be listed for all patients in the randomized population.

8.4. Smoking and Alcohol History

Smoking and alcohol history will be summarized for the ITT population using standard descriptive statistics and listed for all patients in the randomized population.

8.5. Medical History

Medical history, including surgical history will be coded using Medical Dictionary for Regulatory Activities (MedDRA) 24.0. Medical history and ongoing conditions will be summarized in separate tables for the ITT population presenting the number and percentages of patients within each preferred term (PT) grouped by the system organ class (SOC). A patient with multiple occurrences of an event in a PT is counted only once. Medical history will be listed for all patients in the randomized population.

8.6. Medication

The WHO Drug, March 2021, B3 will be used to classify prior and concomitant medications by therapeutic class and drug name.

Prior medication is defined as any medication taken before the date of the first dose of study treatment. Concomitant medication is defined as any medication taken on or after the date of the first dose of study treatment.

The use of prior medications, concomitant medications, and concomitant disallowed medications will be summarized by the number and percentage of patients for the ITT population. If a patient takes a specific medication multiple times or takes multiple medications within a specific therapeutic class, that patient would be counted only once for the coded drug name or therapeutic class.

A table will be provided showing patients receiving disallowed medications that may influence efficacy assessments at any time during the initial 16-weeks (e.g. topical treatments, systemic treatments, biologics or phototherapy)

A figure will be provided with the cumulative proportion of patients over time receiving disallowed medication that may influence efficacy assessments. Patients will count as receiving disallowed medication that may influence efficacy from first initiation.

Prior medications, concomitant medications, and concomitant disallowed medications will be listed for all patients in the randomized population.

A summary table will be provided for previous treatments for atopic dermatitis (e.g. prior systemics, biologics). Previous treatments for atopic dermatitis and reasons for stopping previous treatments for atopic dermatitis will be summarized for the ITT population. Previous treatments for atopic dermatitis will be listed for all patients in the randomized population.

8.7. Extent of Exposure

Study drug administration data, study drug accountability data, and study drug compliance check data will be listed for all patients in the ITT population.

8.8. Treatment Compliance

When patients receive the study drug at the site, they will receive it directly from the investigator or designee who will also give instruction for dose administration. The date of study drug dispensed to the patients will be recorded. At all site visits, patients will return all study drug, including packaging, dispensed at the previous visit.

The dose of study drug and study patient identification will be confirmed at the time of administration by a member of the study site staff other than the person administering the study drug.

When patients self-administer the study drug at home, compliance with the protocol will be assessed at each visit. Compliance will be assessed by direct questioning and counting returned tablets during the site visits. Deviation from the prescribed dosage regimen should be recorded.

A record of the quantity of study drug dispensed to and administered by each patient must be maintained and reconciled with study drug and compliance records. Study drug administration dates, including dates for administration delays and/or dose reductions will also be recorded.

Number of patients with missed doses, number of missed doses, reasons for dose interruption, duration of exposure, compliance rate and compliance rate until treatment discontinuation will be summarized overall by treatment group for the ITT population and separately for the titration period.

9. Efficacy

For inferential analyses of primary and secondary efficacy endpoints, each active treatment group will be compared with the placebo group.

Patients who receive topical medications will be allowed to continue with study treatment while patients receiving systemic medication will be discontinued from study treatment. This means that some patients (particularly in the less effective arms) will have efficacy assessments collected after receiving topical medicals which may influence efficacy assessments.

To ensure that the primary analyses evaluate the effect of study treatment (and not the effect of study treatment + disallowed medications (e.g. topical medications) the following approach will be taken: Patients efficacy data collected after date of first disallowed medication (which may influence efficacy assessments e.g. any medication given to control unacceptable atopic dermatitis symptoms) will be first 'set to missing' / 'treated as missing'. If disallowed medication is introduced the same day as an efficacy assessment, the efficacy assessment will be used as is. Thereafter, the below described analyses should applied.

Primary and secondary efficacy endpoints are to be assessed in the ITT Population. Missing data and data 'treated as missing' for the primary analysis of primary and secondary binary endpoints will be handled with the following multiple imputation method: Intermittent missing data will first be imputed using the MCMC method implemented with the SAS MI procedure, which is appropriate for non-monotonic missing data. Data missing (including 'treated as missing') will then be multiply imputed with the SAS MI procedure using a regression statement (number of imputations: 50, seed: 3628479. At each time point, missing data will be assumed to be MAR and to follow a distribution similar to scores for patients who are still in the study and randomized to the same treatment group.

For categorical efficacy endpoints based on a continuous variable, the multiple imputation will be first done for the continuous variable, then determine the category using the imputed values. Efficacy analyses will be repeated on the PP Population for primary and key secondary endpoints.

When appropriate, the raw parameter, its change from Baseline, and percentage change from Baseline will be summarized.

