#### 10.1.2 The Investigator Global Assessment for Atopic Dermatitis

The IGA-AD is a measure used by physicians to determine a patient's overall severity of disease. The static version is used in this trial for measurement at a single point in time, as indicated in the Schedule of Assessments (Table 4). The Investigator will rate the severity of the patient's AD on a 5-point scale ranging from 0 (clear) to 4 (severe) (Simpson E, 2020).

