4.2. Patient Selection

4.2.1. Inclusion Criteria

Patients are eligible to be included in the study only if all the following criteria apply at both the screening and baseline visits:

- 1. Capable of giving signed informed consent, which includes compliance with the requirements and restrictions listed in the Informed Consent Form (ICF) and in the protocol.
- 2. Male and female patients aged at least 18 years at the time of signing the ICF.
- 3. Body weight of greater than 40 kg at the time of signing the ICF.
- 4. Diagnosis of AD for a minimum of 1 year (before the Screening visit) using the Hanifin and Rajka criteria.
- 5. Moderate to severe AD (affected BSA of at least 10%, IGA-AD grade of at least 3, and EASI score of at least 16) at the screening and baseline visits.
- 6. Candidate for systemic treatment or phototherapy for AD.
- 7. Patients having a documented history of inadequate response to treatment with topical medications given for at least 4 weeks (at least 2 weeks for high potency topical corticosteroids), or as labeled, or for whom topical treatments are otherwise medically inadvisable.

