5.2. Secondary Efficacy Endpoints

Key Secondary Efficacy Endpoints:

- Patients achieving 75% reduction in EASI (EASI75) response at Week 16.
- Patients achieving a score of clear (0) or almost clear (1) and at least a 2-point improvement in IGA-AD at Week 16.

Other Secondary Efficacy Endpoints:

- Patients achieving a score of clear (0) or almost clear (1) and at least a 2-point improvement in IGA-AD at Weeks 2, 4, 8, 12, and 20.
- Patients achieving EASI75 at Weeks 2, 4, 8, 12, and 20.
- Patients achieving 50% reduction in EASI (EASI50) and 90% reduction in EASI (EASI90) response at Weeks 2, 4, 8, 12, 16, and 20.
- Percent change from Baseline in EASI at Weeks 2, 4, 8, 12, and 20.
- Change from Baseline in the peak pruritus NRS score at Weeks 1, 2, 4, 8, 12, 16, and 20.
- Patients achieving at least a 4-point improvement in the peak pruritus NRS from baseline at Weeks 1, 2, 4, 8, 12, 16, and 20 among patients with a baseline score ≥4.
- Change from Baseline in affected BSA at Weeks 2, 4, 8, 12, 16, and 20.
- Change from Baseline in DLQI score at Weeks 8, 16, and 20.
- Change from Baseline in POEM score at Weeks 2, 4, 8, 12, 16, and 20.
- Change from Baseline in PGIS score at Weeks 2, 4, 8, 12, 16, and 20.
- PGIC score at Weeks 2, 4, 8, 12, 16, and 20.
- Change from Baseline in sleep disturbance NRS score at Weeks 1, 2, 4, 8, 12, 16, and 20.
- Change from Baseline in skin pain NRS score at Weeks 1, 2, 4, 8, 12, 16, and 20.

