	14.2.2.2.1	Patients achieving a Score of Clear (0) or Almost Clear (1) and an at least 2-point improvement in Investigator Global Assessment for AD (IGA-AD) at Week 16. Key Secondary Efficacy Analysis: Multiple Imputation	ITT Population
	14.2.2.2.2	Patients achieving a Score of Clear (0) or Almost Clear (1) and an at least 2-point improvement in Investigator Global Assessment for AD (IGA-AD) at Week 16. Key Secondary Efficacy Analysis: Multiple Imputation	PP Population
	14.2.2.3	Patients achieving a Score of Clear (0) or Almost Clear (1) and an at least 2-point improvement in Investigator Global Assessment for AD (IGA-AD) at Week 16. Key Secondary Efficacy Analysis: Non- response Imputation for missing data and data treated as missing	ITT Population
	14.2.2.2.4	Patients achieving a Score of Clear (0) or Almost Clear (1) and an at least 2-point improvement in Investigator Global Assessment for AD (IGA-AD) at Week 16. Key Secondary Efficacy Analysis: Non- response Imputation for missing data	ITT Population
	14.2.2.2.5.1	Patients achieving a score of Clear (0) or Almost Clear (1) and an at least 2-point improvement in Investigator Global Assessment for Atopic Dermatitis (IGA-AD) at Week 16 by Baseline IGA Key Secondary Efficacy Analysis: Descriptive Statistics	ITT Population

Header	Table Number	Name	Analysis Population
	14.2.2.2.5.2	Patients achieving a score of Clear (0) or Almost Clear (1) and an at least 2-point improvement in Investigator Global Assessment for Atopic Dermatitis (IGA-AD) at Week 16 by Body Weight at Baseline	ITT Population
		Key Secondary Efficacy Analysis: Descriptive Statistics	
	14.2.2.2.5.3	Patients achieving a score of Clear (0) or Almost Clear (1) and an at least 2-point improvement in Investigator Global Assessment for Atopic Dermatitis (IGA-AD) at Week 16 by Region Key Secondary Efficacy Analysis: Descriptive Statistics	ITT Population
	14.2.2.2.6.1	Patients achieving a score of Clear (0) or Almost Clear (1) and an at least 2-point improvement in Investigator Global Assessment for Atopic Dermatitis (IGA-AD) at Week 16 by Baseline IGA Key Secondary Efficacy Analysis: Non- response Imputation for missing data and data treated as missing	ITT Population

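### The SAP sends IGA-AD, a five-grade ordinal score, through normal-theory multiple imputation and gives no ordinal model, rounding rule or range, so the imputed response rate rests on an unstated choice

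*SAP*

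**What the plan says.** SAP Section 9 states that missing data, including data set to missing after a first disallowed medication, "for the primary analysis of primary and secondary binary endpoints will be handled with the following multiple imputation method": MCMC for intermittent gaps, then data missing "will then be multiply imputed with the SAS MI procedure using a regression statement", with 50 imputations, assumed missing at random within treatment group. For categorical endpoints based on a continuous variable it adds that "the multiple imputation will be first done for the continuous variable, then determine the category using the imputed values". SAP Section 7.3 says the same in shorter form.

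The key secondary endpoint in SAP Section 5.2 is "Patients achieving a score of clear (0) or almost clear (1) and at least a 2-point improvement in IGA-AD at Week 16". Protocol Section 10.1.2 has the investigator rate IGA-AD as one of five grades, 0 to 4. In the SAP Section 18 index, Table 14.2.2.2.1 for this endpoint carries the subtitle "Key Secondary Efficacy Analysis: Multiple Imputation", in the ITT population. SAP Section 9.2.1 repeats the analysis with missing data counted as non-response, as supportive work.

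Neither document names a logistic or ordinal imputation model, a rounding rule, a minimum or maximum, or a cut-off for an imputed IGA-AD value.

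**The concern.** MCMC in PROC MI assumes a multivariate normal model, and a regression statement in the same procedure draws from a linear model with normal residuals. Both return real numbers. For EASI that does little harm, because EASI50, EASI75 and EASI90 are thresholds on a near-continuous score. For a five-grade score, draws land between grades and can fall below 0 or above 4, so someone must decide whether 1.3 is a success.

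The cut alone decides the outcome. Inclusion criterion 5 requires a baseline IGA-AD of at least 3, so any grade of 0 or 1 already meets the 2-point condition. The sentence on impute-then-categorise does not help, because it covers endpoints based on a continuous variable and IGA-AD is not one.

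At stake is the primary analysis of one of two key secondary endpoints in a trial meant to choose a Phase 3 dose.

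**Working it through.** **The plan's own figure.** The only design calculation is for EASI: difference 25, SD 43, two-sided 5%, 80% power (SAP Section 4.3). n per arm = 2 × (1.960 + 0.842)² × 43² / 25² = 46.4, so 47. Power at 47 is 80.5% by the normal approximation and 79.6% by the noncentral t. This reproduces the plan. About 210 randomized over four arms gives 52 to 53 per arm. The documents give no IGA-AD response rate, and the only missing-data figure is dropout of about 10%. Everything below on IGA-AD therefore rests on assumed distributions.

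**Marginal check.** Take an assumed Week 16 distribution over grades 0 to 4, match a normal to its mean and SD, and compare P(X ≤ 1) (unrounded) and P(X < 1.5) (rounded to the nearest grade) with the true rate.

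- Active, 7/18/30/33/12%, true response 25%. Mean 2.25; variance 6.27 − 2.25² = 1.2075; SD 1.10. Unrounded: Φ((1 − 2.25)/1.099) = 12.8%. Rounded: Φ((1.5 − 2.25)/1.099) = 24.7%.
- Placebo, 3/7/20/45/25%, true response 10%. Mean 2.82; variance 8.92 − 2.82² = 0.9676; SD 0.98. Unrounded: Φ((1 − 2.82)/0.984) = 3.2%. Rounded: Φ((1.5 − 2.82)/0.984) = 9.0%.

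Across other assumed distributions with true rates of 5 to 40%, the unrounded cut gives 0.20 to 0.55 of the truth and the rounded cut 0.84 to 0.96.

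**Effect on the whole arm, unrounded cut.** Loss = missing share × (true − imputed rate).

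- 10% missing in both arms: active 0.10 × (25 − 12.8) = 1.2 points; placebo 0.10 × (10 − 3.2) = 0.7. The 15-point difference shrinks by about 0.5.
- With true rates of 30% (imputed 15.4%) and 10%: losses of 1.5 and 0.7, so a 20-point difference shrinks by about 0.8. At 30% missing the losses are 4.4 and 2.0, a shrinkage of about 2.3.
- Unequal missingness, 15% on active and 35% on placebo, first pair of distributions: losses of 0.15 × 12.2 = 1.8 and 0.35 × 6.8 = 2.4. The difference now grows by about 0.6.

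**Regression on earlier visits.** A simulation used 53 patients per arm, five post-baseline visits, latent autoregressive correlation 0.7, monotone MAR dropout, within-arm sequential linear regression, 10 imputations and 300 replicates. Ratios are imputed to true responders among imputed patients, over assumed true rates of 5 to 40%:

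| Missing | Unrounded, cut at 1 | Rounded |
|---|---|---|
| 16–20% | 0.48–0.63 | 0.97–1.32 |
| 33–41% | 0.60–0.69 | 0.97–1.74 |

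The excess after rounding is largest at low response rates. For the arms with assumed rates of 30% and 10%:

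| Missing (active, placebo) | True | Unrounded | Rounded |
|---|---|---|---|
| 17%, 19% | 29.4 − 10.0 = 19.4 | 27.6 − 9.3 = 18.3 | 29.3 − 10.5 = 18.8 |
| 35%, 39% | 30.0 − 10.3 = 19.7 | 26.5 − 9.3 = 17.2 | 30.2 − 11.7 = 18.5 |

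**Against sampling error.** With 52 per arm and rates of 25% and 10%, the standard error of the difference is √(0.25 × 0.75/52 + 0.10 × 0.90/52) = 7.3 points.

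**The case against.** A reader might infer that the SAP will count imputed patients as responders far too rarely, understating response in every arm and shrinking every treatment difference. The documents do not support that. Nothing in the SAP says that an imputed IGA-AD value is cut at 1 without rounding. If draws are rounded, the marginal shortfall nearly disappears, and in the simulation it becomes an excess at low rates. The direction for the treatment difference is not fixed either, since it reverses when placebo has enough additional missing data.

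There is a further case on the other side:

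- The SAP never uses the word linear, and it expects imputed data to resemble observed scores in the same arm, which fractional or negative grades would not. The table shells, a separate document, may say more. This leaves room for a sensible implementation, but a regression statement in PROC MI is ordinarily the linear one, and nothing in the text points to an ordinal model.
- The size is small. A shift of 0.5 to 0.8 points at 10% missing is about a tenth of a standard error. This stands.
- Two non-response analyses in SAP Section 9.2.1 avoid imputation models altogether, and all p-values are nominal (SAP Section 7.1). This also stands. But those analyses are supportive, and they do not settle what the primary analysis of this endpoint is.

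**Conclusion.** The point holds as a mismatch between method and scale, together with an unstated rule. It does not hold as a demonstrated bias in one direction. One programming choice left open by the SAP changes the imputed response rate by a factor of about two on active and nearly three on placebo in the marginal model. Rounding is close to neutral there but not reliably so in regression imputation.

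The consequence is bounded by the missing share: about 1 point or less on the treatment difference at the planned 10% dropout. The share could be larger, because SAP Section 9 also sets to missing everything after a first disallowed medication and expects topical use particularly in the less effective arms. No figure in the documents says how much larger. The grade distributions, the correlation and all missing shares above 10% are assumptions.

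This is a cheap improvement, not a threat to the trial's conclusions.

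**What to change.** Amend SAP Sections 7.3 and 9 before unblinding:

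- Impute IGA-AD within treatment arm with an ordinal model: PROC MI with a monotone or FCS logistic statement (cumulative logit), using baseline and earlier IGA-AD as predictors. If the monotone form is chosen, the intermittent gaps also need an ordinal step, because MCMC would again give fractional grades. FCS handles both together.
- Derive response from the imputed grade.
- State in advance how sparse grades are merged, and name a fallback if the model does not converge: impute the binary response by logistic regression.
- Keep the regression method for the EASI-based responders. Peak pruritus NRS is an 11-point integer scale (Protocol Section 10.2.1), so if its responder endpoint stays on the regression method, state rounding and a 0 to 10 range. Otherwise an imputed improvement of 3.6 points raises the same question.

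If an ordinal model is not adopted, the minimum is a written rounding and range rule for IGA-AD.

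The cost is one SAP paragraph and a changed PROC MI statement. The drawback is sparse grades with about 52 patients per arm, especially at early visits, which is why the merging rule and fallback belong in the text.
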